### **7.4 Final Study Visit (End-of-Study Follow-up Visit) – Days 12 to 18**

Parents/legal guardians and their children will be asked to return once during Days 12 to 18 for a routine follow-up evaluation. At this visit, the PRSS will be completed and parents will be questioned regarding the child quality of life. A nasopharyngeal swab will be obtained, when possible, and placed in transport media and sent to the Microbiology Laboratory-CHP for processing. In the event a nasopharyngeal swab is unable to be obtained, the study team will obtain a mid-turbinate nasal swab. We will ask about adverse events, interim medical history including visits to other health care providers, and concomitant medications. A phone call, email or text message will be sent 1 to 2 days before the end-of-study follow-up visit to confirm the time of the appointment. If the patient is unable to come to the end-of-study follow-up visit, a visit to the home will be offered. If this is not possible, we will, to the extent possible, obtain information that was to be gathered at the Final Study Visit by phone or email.

## **7.5 Unscheduled Visit (Interim (Sick) Visit)**

If a child's PRSS score is not improving as expected, or if a parent is concerned about their child, an interim evaluation will be scheduled, usually on the same day. If the parent/legal guardian is unable to come to the office, a home visit may be offered. If the child cannot be seen and assessment of the child's symptoms by phone indicate that the child is not acutely worsening and no new symptoms are reported, an antibiotic may be started without an evaluation. A study team member will be available 24 hours/day, 7 days/week via cellular phone. Children failing study product will be treated with clindamycin plus cefixime, amoxicillin-clavulanate potassium, levofloxacin, or a similar antibiotic, as clinically indicated and without breaking the blind. The results of the nasopharyngeal culture may be used to guide therapy. The following procedures may be performed at this visit: interim medical history including visits to other health care providers and concomitant medications collection, temperature measurement, face/nose assessment, PRSS score, and adverse events monitoring. Temperature will be measured using appropriate method according to the child's age and parental preference (oral, rectal, axially, temporal, or tympanic).

## 8 STUDY PROCEDURES/EVALUATIONS

### 8.1 Clinical Evaluations

**Medical History:** Will be obtained by interview of the parents/legal guardians. Parents/legal guardians will be queried regarding demographic characteristics, risk factors (day care attendance, exposure to smokers in the house), symptoms (type and duration, including some symptoms not included on the PRSS), and past medical history since birth (sinusitis, allergic rhinitis, asthma, and medications used to treat these) at the baseline visit. We will also ask parents/legal guardians to assess the severity of their child's symptoms using a visual analog scale anchored at "very mild" and "very severe". At the final end-of-study follow-up visit, we will ask parents to complete the PRSS, to answer question about visits to other providers, missed work, quality of life, and the need to make alternate daycare arrangements, and about adverse events.

**Medication History:** Will be obtained by interview of the parents/legal guardians. We will ask about previous antihistamines, decongestant, albuterol, or corticosteroid use during the past 7 days and antibiotics use up to 3 months before enrollment. We also track the use of these same medications along with analgesic medication through the end-of-study follow-up visit or early termination, whichever occurs first. Receipt of a systemic antibiotic while taking study medication will be recorded as this constitutes a secondary endpoint of the study. The use of these medications will be ascertained by parent/legal guardian interview at the end-of-study follow-up visit or early termination, whichever occurs first.

**Vital Signs:** Temperature and weight will be measured at enrollment/baseline visit and the interim (sick) visit (if not already taken for clinical care). Temperature will be measured using appropriate method according to the child's age and parental preference (oral, rectal, axially, temporal, or tympanic).

**Limited assessment of face and nose:** At the baseline and unscheduled interim (sick) visit, a targeted assessment of the face and nose using standardized methods will be performed by appropriate study personnel.

**Diary:** The PRSS will be administered by parents/legal guardians every evening as an electronic diary. In addition to the PRSS score, the diary will track compliance with study product, the frequency and the consistency of bowel movements, and a global assessment of health. The critical data for symptom resolution is during days 2-11, but we have given parents the opportunity to record the information from day 1 in order to establish the habit of recording in the diary.

### 8.2 Laboratory Evaluations

#### 8.2.1 Clinical Laboratory Evaluations

At the enrollment/baseline and final study visit, a nasopharyngeal sample may be obtained from one nostril using a sterile, flexible, thin, flocked swab. Compared to Dacron swabs, flocked swabs are better tolerated and have a higher yield for bacteria and viruses. The tip of the nose

will be raised and the swab introduced gently along the floor of the nasal cavity, close to the nasal septum, until the pharyngeal wall is reached. If any obstruction is encountered, the sample will be taken from the other nostril. All investigators will be trained on this procedure before to the onset of the study (see protocol-specific Manual of Procedures). We will cut the tip of the swab with a pair of sterile scissors into a cryovial containing RLT and this will be stored for future studies of RNA expression. The remainder of the swab will be placed into Amies and will be refrigerated (2-8° C) until it can be transported (on ice) to the Microbiology Laboratory at Children's Hospital of Pittsburgh (within 48 hours). Two types of culture plates will be used initially: trypticase soy 5% sheep blood agar and chocolate agar. Cultures will be incubated overnight at 37°C with 5% CO2. If no growth is present after overnight incubation, the culture will be re-incubated for an additional 24 hours. Identification of *S. pneumoniae*, *H. influenzae*, *M. catarrhalis* and *Streptococcus pyogenes* will be performed using standard semiquantitative techniques. For isolates thought to be *H. influenzae* that will be subcultured on a *Haemophilus* ID Quad plate. These isolates will be typed and if found to be non typeable, confirmed to be *H. influenzae* by PCR. In addition, we will test for β-lactamase production using a cefinase test on selective agar. Isolates considered to be *M. catarrhalis* will undergo subculture and identification will be confirmed using the Remel Catarrhalis Test Disk. Isolates considered to be *S. pneumoniae* will undergo subculture on a TSA blood agar plate. Susceptibility testing will be done on all isolates using the Vitek system. Isolates will be considered nonsusceptible to penicillin according to the most current guidelines from the Clinical Laboratory Standards Institute (CLSI). Microdilutional broth susceptibility testing will be performed on all penicillin non susceptible isolates. All pneumococcal isolates will be typed using gene-based typing methods.

## 8.2.2 Special Assays or Procedures

Not applicable.

## 8.2.3 Specimen Preparation, Handling, and Shipping

### 8.2.3.1 Instructions for Specimen Preparation, Handling, and Storage

All clinical microbiological samples (NP swab and MT swab specimens) obtained from all study participants enrolled at all participating clinical study sites will be processed at CHP according to guidelines established by the Microbiology Laboratory. This laboratory will identify all organisms cultured from the samples. Instructions for specimen preparation, handling, and storage are included in the Laboratory Plan.

### 8.2.3.2 Specimen Shipment

NP swab (or MT swab) specimens may be collected at the entry visit (Day 1) and the follow-up visit (Day 12-18). Specimens will be placed in a transport tube with a study label. Specimens are transported to the Microbiology Laboratory at CHP at intervals of every 3 hours for CHP of UPMC sites. Specimens from PittNet PBRN sites will be refrigerated and sent via courier to the Microbiology Laboratory at CHP within 48 hours. Specimens from all other sites will be mailed on the day of collection to the Microbiology Laboratory at CHP. Specimen shipments will be recorded in a specimen-tracking log.

The NP or MT swab specimens will be sent to:  
Children's Hospital of Pittsburgh  
Microbiology Laboratory B228  
[name]  
[name]

Instructions for specimen shipment are included in the Laboratory Plan.

## 9 ASSESSMENT OF SAFETY

### 9.1 Specification of Safety Parameters

We will track common and important adverse events linked with the study product [i.e., Protocol-Defined Diarrhea (PDD), generalized rash, and bacterial resistance], any adverse event, which requires more than minimal medical intervention (see below for definitions), and all serious adverse events.

Because the study product is approved for use for children with sinusitis, we will only track 1) common or important adverse events linked with the study product (PDD, generalized rash), 2) severe adverse event (AEs which require more than minimal medical intervention, Table 4, below), and 3) serious adverse events (see section 9.2.3). PDD will be defined by the occurrence of three or more watery stools in 1 day or two watery stools daily for at least 2 days.

The occurrence of these AEs will be recorded from the first study intervention, Day 1 (enrollment), through the end-of-study follow-up visit.

### 9.2 Methods and Timing for Assessing, Recording, and Analyzing Safety Parameters

#### 9.2.1 Adverse Events

**Adverse Event (AE):** ICH E6 defines an AE as any untoward medical occurrence in a patient or clinical investigation subject administered a pharmaceutical product regardless of its causal relationship to the study treatment. An AE can therefore be any unfavorable and unintended sign (including an abnormal laboratory finding), symptom, or disease temporally associated with the use of medicinal (investigational) product. The occurrence of an AE may come to the attention of study personnel during study visits and interviews of a study recipient presenting for medical care, or upon review by a study monitor. FDA defines an AE as any untoward medical occurrence associated with the use of a drug in humans, whether or not considered drug related.

AEs not meeting the protocol-defined criteria for SAEs will be captured on the appropriate electronic case report form (eCRF). Information to be collected for non-serious AEs includes event description, date of onset, licensed study physician's assessment of severity and relationship to study product and alternate etiology (if not related to study product) (assessed only by those with the training and authority to make a diagnosis and listed on the Form FDA 1572 as the site principal investigator or sub-investigator), date of resolution of the event, seriousness and outcome. AEs occurring during the collection and reporting period will be documented appropriately regardless of their relationship to the study product. All recorded AEs will be followed to adequate resolution. Any medical condition that is present at the time that the subject is screened will be considered as baseline and not reported as an AE. However, if the severity of any pre-existing medical condition increases at any time during the study, it will be recorded as an AE. AEs must be graded for severity and assessed for relationship to study product (see definitions below). Adverse events characterized as intermittent require

documentation of onset and duration of each episode. The start and stop date of each reported AE will be recorded on the appropriate eCRF. Bacterial resistance will be reported based on the report from the laboratory.

**Severity of Event:** AEs will be assessed by a licensed study physician listed on the Form FDA 1572 as the site principal investigator or appropriate sub-investigator. The severity of non-serious AEs will be assessed according to the scale below:

- **Mild:** events require minimal or no treatment and do not interfere with the subject's daily activities.
- **Moderate:** events result in a low level of inconvenience or concern with the therapeutic measures. Moderate events may cause some interference with functioning.
- **Severe:** events interrupt a subject's usual daily activity and may require systemic drug therapy or other treatment. Severe events are usually incapacitating.

Examples of the types of non-serious AEs that will be collected (contained within the heavy lines) and AEs that will not be collected (gray font and marked by an asterisk) are shown in the Table below.

Table 4. Procedure for Recording of Non-Serious Adverse Events

Non-Serious Adverse Events			
	Mild	Moderate	Severe
Rash	*Localized	Generalized and moderate	Generalized and severe (e.g., severe urticaria; serum sickness; Stevens-Johnson Syndrome)
Diarrhea	*Loose stools	3 or more watery stools in 1 day or 2 watery stool daily for at least 2 days (i.e., PDD)	Diarrhea requiring rehydration therapy and is incapacitating
All other Adverse Events	*Requires minimal or no treatment and does not interfere with daily activities	*Requires some treatment and may interfere with daily activities	Requires systemic drug therapy and is clearly incapacitating
Bacterial resistance	N/A	N/A	All bacterial resistance will be collected

\*AEs that will not be collected

**Relationship to Study Products:** The study physician's assessment of an AE's relationship to the study product is required prior to unblinding and is part of the documentation process, but it

is not a factor in determining what is or is not reported in the study. Factors to consider in determining a causal relationship include whether: (1) the event is described in the product insert; (2) a temporal relationship exists between the event and administration of study product; (3) a possible alternative etiology has been identified; and (4) it is biologically plausible that the event may be related to the product. If there is any doubt as to whether a clinical observation is an AE, the event should be reported. In a clinical trial, the study product must always be suspect. The relationship to study product must be assessed for AEs using the terms: related or not related. The following guidelines will be used in this assessment:

- **Related** – There is a reasonable possibility that the study product caused the adverse event. Reasonable possibility means that there is evidence to suggest a causal relationship between the study product and the adverse event.
- **Not Related** – There is not a reasonable possibility that the administration of the study product caused the event.

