	
1) Proportion with adverse events (including emergence of bacterial resistance). 2) Proportion who are compliant with study product (took <math>\geq 70\%</math> of the doses).
 
Flow of patients: We will review each child's PRSS scores every morning and will contact parents/legal guardians of children whose PRSS scores are not improving at the expected rate (see definition of treatment failure above). These children will be seen by the study team and rescue medication will be prescribed, as clinically indicated and without breaking the blind, but they will be continued to be followed in the same way (electronic daily diary and routine end-of-study follow-up visit).
 
Statistical methods:
 
The primary efficacy analyses will be:
 
 
• To determine whether the effect of treatment differs in children with and without nasopharyngeal colonization with respiratory pathogens (i.e., we will test for interaction).
 
• To determine whether the effect of treatment differs in children with and without colored nasal discharge (i.e., we will test for interaction).
 
 
Generalized estimating equations will be used for these analyses. The primary analysis will be based on the intention-to-treat principle and will use two-sided tests. The variables chosen to define the subgroups were based on extensive preliminary data indicating likely heterogeneity of treatment effect in subpopulations defined by the presence/absence of these variables. This sample size will allow us to test these 2 hypotheses simultaneously.

Laboratory Tests:
	
A nasopharyngeal swab (or mid-turbinate nasal swab if a nasalpharyngeal swab is unable to be obtained) will be obtained at the baseline and final visit from all participants, when possible. We will use the presence of respiratory pathogens as one of the subgrouping variables. These swabs will be shipped to the Microbiology Lab at the Children's Hospital of Pittsburgh (CHP) on ice within 48 hours. According to the preliminary data presented, shipping of swabs does not adversely affect the ability to recover the respiratory pathogens being investigated. The Microbiology Lab will identify S. pneumoniae, H. influenzae, and M. catarrhalis using standard microbiological techniques.

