#### **2.2.5 Rationale for the use of clavulanate**

In our preliminary data, 48% of *H. influenzae* isolates and 100% of *M. catarrhalis* isolates produced  $\beta$ -lactamase. Furthermore, the incidence of disease caused by *H. influenzae* may be increasing secondary to routine vaccination with pneumococcal conjugate vaccine. Thus, the use of amoxicillin-clavulanate potassium instead of amoxicillin alone seems prudent. The most recent guideline from the Infectious Diseases Society of America (IDSA) recommends amoxicillin-clavulanate potassium as the preferred agent for sinusitis in children. The AAP guideline recommends using amoxicillin with or without clavulanate potassium as the first-line agent.

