### 3.2.3 Tertiary outcomes

#### Safety Outcomes

- 1) Adverse events - The proportions of children experiencing adverse events will be compared. We will also track the duration of each reported adverse event. This will include a comparison of the number of children at the follow-up visit who have resistance organisms. Diarrhea will be defined as the occurrence of  $\geq 3$  watery stools in 1 day or 2 watery stools per day for 2 consecutive days, and will be tracked in the daily diary.
- 2) Compliance - In the daily diary, we will ask parents/legal guardians to record whether they administered the doses of study product. Administration of  $\geq 70\%$  of the doses will be considered compliant.

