#### **9.2.4 Procedures to be Followed in the Event of Abnormal Laboratory Test Values or Abnormal Clinical Findings**

NP specimens will be obtained for culture at baseline and follow-up for the identification of *S. pneumoniae*, *H. influenzae*, and *M. catarrhalis*. Detection of *S. pneumoniae*, *H. influenzae*, and *M. catarrhalis* in the nasopharynx will be considered a normal finding.

Study product may need to be discontinued in subjects with a clinical adverse event, laboratory abnormality, intercurrent illness, or other medical condition such that continuation of study product would not be in their best interest. Randomization codes will not be broken at any time in the event of treatment failure unless deemed necessary for medical /emergency/safety reasons. These subjects will be asked to continue to record their symptoms on the PRSS on a daily basis and to return to the clinic for a routine end-of-study follow-up visit to be held once during Days 12 to 18.

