### **11.10.2 Adverse Events**

The number of patients with adverse events will be tabulated by treatment group. The number of patients experiencing each adverse event will also be summarized by severity and relationship to study drug. If an adverse event is reported more than once during the study period for a given patient, the greatest intensity will be presented in the tables. For summary tables, adverse events will be grouped by organ system. We will also track the duration of each reported adverse event. Diarrhea, a key and expected adverse event, will be defined as the occurrence of  $\geq 3$  watery stools in 1 day or 2 watery stools per day for 2 consecutive days, and will be tracked in the daily diary. The incidence of serious adverse events and study medication discontinuation due to adverse events will also be compared using Fisher's exact test. Data listings and narratives will be provided for patients discontinuing treatment due to adverse events and patients with serious adverse events.

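### Table 4 grades all bacterial resistance as Severe whatever the symptoms, and the follow-up count in section 3.2.3 does not measure emergence of resistance

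*Combined protocol and SAP*

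**What the plan says.** **Grading.** Section 9.1 lists the adverse events to be tracked as "Protocol-Defined Diarrhea (PDD), generalized rash, and bacterial resistance"; its next paragraph repeats the list without resistance. Section 9.2.1 requires every AE to be graded. In Table 4 the resistance row reads N/A under Mild, N/A under Moderate, and "All bacterial resistance will be collected" under Severe. The severity scale just above the table says "Severe events are usually incapacitating", and section 9.1 describes severe AEs as those needing more than minimal medical intervention. Section 9.2.1 takes resistance from the laboratory report and attaches no clinical criterion.

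**Outcome.** The Protocol Summary gives the tertiary outcome as "Proportion with adverse events (including emergence of bacterial resistance". Sections 3.1 and 11.2 speak of the development of resistance. Section 3.2.3 makes the outcome a "comparison of the number of children at the follow-up visit who have resistance organisms".

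**Baseline.** Section 9.2.1 treats a medical condition present at screening as baseline and not as an AE unless it worsens. Section 11.5 tabulates how resistance changes between the two visits.

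**Reporting.** Section 11.10.2 tabulates patients with AEs by arm and adds: "The number of patients experiencing each adverse event will also be summarized by severity and relationship to study drug". A patient with repeated reports of an event is shown at the greatest intensity.

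**The concern.** Two separate things go wrong.

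First, resistance is a property of an isolate, not of the child's clinical state. Once it is an AE it must receive a grade, and Table 4 leaves only Severe. A child who is well but whose swab grows a resistant organism then sits in the same column as a child with incapacitating diarrhea. Pooled any-AE and severe-AE totals can be inflated by findings with no symptoms, and under section 9.3 the recorded AEs also go to the DSMB.

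Second, the count in section 3.2.3 is a prevalence at Days 12 to 18. It includes resistant carriage that was there on Day 1 and persisted, and it omits resistant carriage that was cleared. Emergence is a different quantity. An antibiotic may both clear existing carriage and select new resistance, and a single prevalence count cannot separate the two. The trial exists partly to weigh benefit against harms such as resistance, so the resistance comparison should have a direction that can be interpreted.

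**Working it through.** The plan states no figure for this point, so there is none to reproduce. The check has three parts.

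**1. The passages side by side**

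- Severe by definition (9.2.1): interrupts usual activity, usually incapacitating. Severe by Table 4: any resistance in the laboratory report. These cannot both be the rule.
- Emergence (Protocol Summary), development (3.1, 11.2) and change from baseline (11.5) all need the Day 1 result. The count in 3.2.3 does not use it, and Table 4 says all.
- The baseline rule in 9.2.1 covers a medical condition. Whether symptom-free carriage is one is not said.
- Section 9.1 both includes and omits resistance as a tracked AE.

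**2. How much resistant carriage there may be at Day 1**

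Inputs: 49% of children had one of the three species isolated (2.1.3); 23% of *S. pneumoniae* isolates were penicillin-nonsusceptible, and 6% of beta-lactamase-negative *H. influenzae* were ampicillin-nonsusceptible (2.2.6); "48% of *H. influenzae* isolates and 100% of *M. catarrhalis* isolates produced" beta-lactamase (2.2.5); about 344 children per arm (section 4). The species mix among carriers is not given, so it is assumed, with one species per carrier.

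Formula: share of children = 0.49 × sum of (species share × resistant fraction).

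- Only penicillin-nonsusceptible *S. pneumoniae* counts, all carriers have it: 0.49 × 0.23 = 0.113, about 39 per arm. This is the maximum under that definition.
- Same definition, one third of carriers have it: 0.113 / 3 = 0.038, about 13 per arm.
- Beta-lactamase and ampicillin nonsusceptibility also count. The *H. influenzae* fraction is then 0.48 + 0.52 × 0.06 = 0.511. With equal species shares: 0.49 × (0.23 + 0.511 + 1.00) / 3 = 0.284, about 98 per arm. With shares of 50/30/20 (*S. pneumoniae*, *H. influenzae*, *M. catarrhalis*): 0.49 × (0.115 + 0.153 + 0.200) = 0.229, about 79 per arm.

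Section 8.2.1 names a criterion for penicillin nonsusceptibility only, so the definition that fixes this number is missing.

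**3. What a follow-up count measures**

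Let b be resistant carriage at Day 1, p the fraction of it that persists, and a the fraction of the other children who acquire resistance. Then:

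- follow-up count = b × p + (1 − b) × a
- new resistance = (1 − b) × a

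All values of b, p and a below are assumptions. Placebo is fixed at p = 0.80, a = 0.03.

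| b | Active p | Active a | Follow-up count, placebo vs active | New resistance, placebo vs active |
|---|---|---|---|---|
| 0.25 | 0.80 | 0.03 | 22.25% vs 22.25% | 2.25% vs 2.25% |
| 0.25 | 0.40 | 0.03 | 22.25% vs 12.25% | 2.25% vs 2.25% |
| 0.25 | 0.40 | 0.08 | 22.25% vs 16.0% | 2.25% vs 6.0% |
| 0.25 | 0.80 | 0.08 | 22.25% vs 26.0% | 2.25% vs 6.0% |
| 0.11 | 0.40 | 0.08 | 11.5% vs 11.5% | 2.7% vs 7.1% |
| 0.04 | 0.40 | 0.08 | 6.1% vs 9.3% | 2.9% vs 7.7% |

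Third row, worked: placebo 0.25 × 0.80 + 0.75 × 0.03 = 0.2225; active 0.25 × 0.40 + 0.75 × 0.08 = 0.160.

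In the third, fifth and sixth rows the drug behaves identically, and new resistance is higher on active each time. The follow-up count nevertheless shows placebo worse, no difference, and active worse. Only baseline carriage changed, and that depends on how resistance is defined.

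**The case against.** The case for leaving the plan alone has substance.

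- **Baseline carriage is largely meant to be excluded.** AE recording starts at the first study intervention (9.1), pre-existing conditions are not AEs (9.2.1), the outcome and objectives say emergence or development, and 11.5 looks at change. A reader might infer that carriage present before dosing will fill the severe-AE tables. The documents do not support that. They are inconsistent: 3.2.3 and Table 4 leave the route open, while the other passages point towards closing it.
- **A reader might also infer that placebo will look less safe.** No figure in the documents shows this. Section 2.3.1 links antibiotics to resistant bacteria, and the table above gives either sign depending on assumed clearance and acquisition.
- **A reader might take the Day 1 figure as high as 49%.** That requires every carrier to have *M. catarrhalis* and beta-lactamase to count. Section 2.1.3 says fewer children carried *H. influenzae* and *M. catarrhalis*.
- **Diarrhea and rash are not hidden.** Section 11.10.2 reports each event separately and groups events by organ system. Its Fisher test concerns serious AEs and discontinuations, and the halting rules in 9.5 do not use severe-AE counts. Only pooled totals are affected, within a tertiary outcome.
- **Table 4 may state a collection rule, not a grade.** It is introduced as giving examples, and its line and font formatting is lost in the text available. But AEs must be graded, the other two cells are N/A, and the entry stands under Severe, so a data manager following the table would code Severe.
- **Section 9.2.4 is not a direct contradiction.** It says that detecting these species "in the nasopharynx will be considered a normal finding", but says nothing about resistance.

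What remains is the grading conflict and the mismatch between a follow-up prevalence and the named outcome.

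**Conclusion.** The point holds in a limited form. As written, Table 4 grades symptom-free resistance as Severe against the protocol's own scale, and the AE outcome carries it into pooled any-AE and severe-AE totals. The count in 3.2.3 does not measure emergence, and its direction between arms cannot be interpreted.

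The size is uncertain because resistance is undefined and the species mix unstated: about 4% to 11% of children at Day 1 under the penicillin-nonsusceptible *S. pneumoniae* definition with the shares shown, and more (23% to 28% in the two mixes worked above) if beta-lactamase counts. These are baseline figures. They bear on the AE totals only to the extent that baseline carriage is counted, which the documents leave unresolved. They also assume that every child is cultured, whereas swabs are taken only when possible. No sample size, power or alpha figure is affected.

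**What to change.** 1. Take bacterial resistance out of the severity grades in Table 4 and out of the pooled proportion with adverse events. Grade symptomatic events by the 9.2.1 definitions as now.
2. Define resistance by organism and drug, and state whether beta-lactamase production counts.
3. Report it as a separate microbiological outcome by arm: a resistant isolate absent at Day 1 and present at Days 12 to 18, among children cultured at both visits. Give the number with paired swabs in each arm.
4. Show carriage and resistance among all children cultured at follow-up descriptively beside it.
5. Align the Protocol Summary tertiary outcomes and sections 3.1, 3.2.3, 9.1, 9.2.1 (Table 4), 11.2, 11.5 and 11.10.2.

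The cost is wording and one tertiary table, since both swabs are already planned. The downside is small: the acquisition analysis uses only children with paired swabs, so it rests on fewer children than were randomized.
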